## Endpoints and outcome measurement

### Primary outcome

- Treatment-related complications that develop within 30 days following ablation will be reported according to the Clavien-Dindo Classification, which is considered the best validated classification to rate surgical complications. The primary outcome is defined as any complication (Grade 2 or above) in the Clavien-Dindo Classification.

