### Secondary outcomes

- Success rate of the procedure is described as rate of complete ablations one month after procedure. A complete ablation response is defined as complete absence of enhancing tissue at the tumor site after one month on CT-scan.
- Complications reported as Comprehensive Complication Index (CCI). CCI is a scoring system for overall morbidity and is reflected on a scale from 0 (no complication) to 100 (death). It is based on Clavien-Dindo classification and takes all complications after a procedure into account.
- Highest complication grade according to the Clavien-Dindo Classification
- Wound infections within 30 days is defined as wound dehiscence requiring secondary suturing or treated conservatively. Fascial dehiscence will be recorded separately.

- Postoperative liver failure is defined by the “50-50 criteria” (prothrombin time <50% and serum bilirubin >50 µmol/L on postoperative day five).
- Postoperative pain will be assessed by Visual Analogue Scale for acute and chronic pain, pre-operatively and on each post-operative day until discharge, after seven days, 14 days and one month.
- Overall and disease-free survival.
- Procedure related mortality within 90 days.
- HRQoL before and one month after the procedure will be assessed using the Danish version of The European Organization for Research and Treatment of Cancer Quality of Life (EORTC QLQ C30) and a disease specific form for patients with HCC (QLQ HCC18), cholangio carcinoma (QLQ BIL21) or colorectal liver metastases (QLQ LM21). Depression and anxiety will be assessed before and one month after procedure using PHQ-9 and GAD-7, respectively. Recovery will be assessed with the Quality of recovery (QoR-15) before and seven days after the procedure.
- Length of hospital stay defined as time in days from operation to discharge.
- Blood loss during surgery
- Need for perioperative blood transfusion
- Conversion rate in the laparoscopic group
- Duration of procedure
- Model for Endstage Liver Disease (MELD) and Child-Pugh score before operation and on postoperative day five.
- Patients experiences of undergoing ablation will be explored by individual interviews one months after the procedure.

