#### 4. Statistical considerations

We will use descriptive statistics and the dataset will be described with frequencies and percentages for categorical variables and means or medians for continuous variables. Primary outcome and rates of secondary dichotomous outcomes will be compared between the groups using Fischer's exact test. Mean VAS score will be compared using Mann-Whitney U-test. To determine risk factors affecting ablation response, logistic regressions will be used in both univariable and multivariable analyses. The EORTC Quality of Life questionnaire is designed to measure cancer patients' social, physical, and psychological functions. Quality of life will be reported using the summary score with the intention of comparing patients treated with either laparoscopic or open ablation. Mann-Whitney U-test will be used to assess differences in the summary scores. Analyses will be performed both on intention-to-treat and per protocol levels. The level of statistical significance will be set to  $p < 0.05$ . All statistical analyses will be performed using R, version 4.0.3.

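### One unadjusted p<0.05 rule covers the primary outcome and about 21–23 possible secondary comparisons in two analysis sets, and complete ablation is sent to a difference test although it is sized as non-inferiority

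*Combined protocol and SAP*

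**What the plan says.** The Primary outcome section names one outcome: "The primary outcome is defined as any complication (Grade 2 or above) in the Clavien-Dindo Classification". The Secondary outcomes section then lists 16 items, from complete ablation and complication scores to survival, pain, quality of life and operative measures.

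Section 4 (Statistical considerations) states:

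- For the primary and the binary secondary outcomes: "Primary outcome and rates of secondary dichotomous outcomes will be compared between the groups using Fischer's exact test".
- For pain: "Mean VAS score will be compared using Mann-Whitney U-test".
- For quality of life: "Mann-Whitney U-test will be used to assess differences in the summary scores".
- On the analysis sets: "Analyses will be performed both on intention-to-treat and per protocol levels".
- On the threshold, which is p<0.05, the sentence opens with "The level of statistical significance will be set to" and gives that one value. Sidedness is not stated, and the rule is not limited to the primary outcome.

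The text available for review gives no ordering of secondary outcomes, no key secondary outcome, no adjustment and no statement of how unadjusted secondary p-values are to be read. Neither analysis set is named as primary.

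Complete ablation is defined as a rate: "Success rate of the procedure is described as rate of complete ablations one month after procedure". The Sample size section sizes it separately as non-inferiority: 95% in both arms, limit 15%, alpha 5%, power 80%, 54 patients.

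**The concern.** With many outcomes, two analysis sets and one threshold, the plan does not say which results would count as evidence and which are supportive. Three features make this matter here.

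- **The primary outcome could well be inconclusive.** The trial is sized on a fall from 45% to 10%. At 40 per arm, exact Fisher power is 93% for that effect. It is 59% if the laparoscopic rate were 20% (an assumed value), and 39% for the external study's 39.5% against that same 20%.
- **Close substitutes are on the list.** The Comprehensive Complication Index and the highest grade are built from the same Clavien-Dindo data as the primary outcome. Nothing in the plan says how to report one of them if it reaches p<0.05 when the primary does not.
- **The two sets can differ.** Section 3 (Method) allows departure from the randomized approach, and the Sample size section plans for conversion above 20%. With no primary set, either p-value could be the one quoted.

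The second strand is complete ablation. Section 6 (Risks) identifies lower treatment success as the main possible disadvantage of laparoscopy, so this is the main safeguard comparison. A non-significant Fisher test could be read as showing similar success, which it does not show.

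**Working it through.** **1. The plan's own figures.**
- Primary outcome, 45% vs 10%, two-sided 5%, power 80%: the two-proportion formula gives 25 per arm without and 30 per arm with continuity correction. The stated 60 patients are reproduced.
- Complete ablation: n per arm = (z_alpha + z_beta)² × 2 × 0.95 × 0.05 / 0.15². At one-sided 5%: (1.645 + 0.842)² × 0.095 / 0.0225 = 26.1, so 27 per arm, 54 in total. This matches. At one-sided 2.5% the result is 33.1, so 34 per arm, 68 in total.

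**2. Counting the secondary comparisons.** Conversion (one arm only) and the interviews (qualitative) are not between-arm comparisons. The rest are:

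| Group | Count |
|---|---|
| Complete ablation | 1 |
| Complication index, highest grade | 2 |
| Wound infection, fascial dehiscence, liver failure | 3 |
| Pain (one pooled test) | 1 |
| Overall survival, disease-free survival, 90-day mortality | 3 |
| QLQ-C30, disease-specific module | 2 |
| PHQ-9, GAD-7, QoR-15 | 3 |
| Stay, blood loss, transfusion, duration | 4 |
| MELD, Child-Pugh | 2 |
| **Total** | **21** |

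The total is 23 if the three disease modules are tested separately. Testing pain at each time point would raise it.

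Section 4 names a test for about eight of these: six binary outcomes (complete ablation, wound infection, fascial dehiscence, liver failure, 90-day mortality, transfusion), pain, and the quality-of-life summary score.

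**3. Chance of at least one p<0.05, one analysis set, every secondary null true.** For k independent tests of exact 5% size the chance is 1 − 0.95^k.
- k = 8: 33.7%
- k = 14: 51.2% (the first k above one half)
- k = 21: 65.9%
- k = 23: 69.3%

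**4. Allowing for Fisher's conservatism and correlation.** At 40 per arm the true size of Fisher's test is 0.01% at a 2% event rate, 0.4% at 5% and 1.7% at 10%. These rates, and all correlations below, are assumptions.
- Eight named tests, independent: about 12% with binary sizes of 0.4% (1 − 0.996⁶ × 0.95²), and about 18% with 1.7% (1 − 0.983⁶ × 0.95²).
- 21 or 23 tests with six binary outcomes at rates of 2–10%: 54.8% or 59.2% if independent; 46.3% or 49.9% at a common correlation of 0.3; 36.5% or 39.0% at 0.5; about 26–27% at 0.7.
- 23 tests all of exact size: 67.6%, 58.3%, 44.8% and 30.8% at common correlations of 0.1, 0.3, 0.5 and 0.7.
- Patient-level simulation of 21 tests, with correlations within/between groups of outcomes of 0/0, 0.3/0.1, 0.5/0.2 and 0.7/0.3: 54%, 51%, 46% and 40%.

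**5. Counting a hit in either analysis set.** With 23 exact-size tests and a correlation of 0.90–0.95 between the two sets' statistics (assumed), the chance is 78–81%, 68–71% and 53–57% at common correlations of 0, 0.3 and 0.5.

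**6. Complete ablation by Fisher's test.** If the true rates were 95% open and 80% laparoscopic, a deficit equal to the limit, Fisher's test at 40 per arm reaches p<0.05 only 41% of the time and misses the difference about 59% of the time. An example with those observed rates is 38/40 against 32/40. Fisher's p is 0.087, so no significant difference. The difference is −15 points with standard error √(0.95×0.05/40 + 0.80×0.20/40) = 0.072, so the lower 90% limit is −0.15 − 1.645×0.072 = −26.8 points. Non-inferiority clearly fails, yet the planned test reports nothing.

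**The case against.** The strongest reply is that the trial has one named primary outcome and labels the rest secondary. The secondary list therefore does not inflate the primary's error rate, and the outcomes are not all presented as equals. That stands.

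A reader might infer that all 21–23 outcomes will be judged at p<0.05. The documents do not go that far. Section 4 opens with descriptive statistics and names tests for about eight secondary outcomes; the rest follows only from the general sentence on significance. Further tests are likely, since Section 2 (Aims) sets out to compare length of stay, but they are not specified.

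A reader might also infer that a false significant secondary finding is more likely than not. This is not established. It needs every secondary null to be true, and either many nearly independent tests of true 5% size or a hit counted in either set. The eight named tests give 34% at most under independence, and the wider count falls on both sides of one half once correlation and rare events are allowed for. Under the trial's own hypothesis, complication-linked outcomes would not be null. A wrong non-inferiority conclusion on complete ablation is also a different kind of error from a spurious difference.

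Finally, nothing in the documents says that an isolated secondary result will be presented as proof of benefit, and Section 13 commits to publishing negative and non-conclusive results. This limits how strongly the harm can be put. It does not supply the missing rule, and it does not touch the mismatch on complete ablation.

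**Conclusion.** The concern holds in a limited form. One unadjusted threshold serves the primary outcome and 21–23 possible secondary comparisons in two sets, with no primary set and no key secondary outcome. If all secondary nulls are true, the per-set chance of at least one false positive is about 34% for the eight named tests (independent, exact size; about 12–18% with Fisher's test on rare events). It rises to 66–69% for 21–23 independent tests. It is about 40–60% in most scenarios with correlation and Fisher's conservatism, and lower under strong common correlation. Event rates and correlations are assumptions, and the figures fall if some nulls are false. The validity of the single primary test is not in question.

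The firmest part needs no such assumptions: Fisher's exact test at p<0.05 cannot answer the non-inferiority question for which complete ablation was sized.

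**What to change.** Rewrite Section 4 (Statistical considerations) so that:

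1. The confirmatory p<0.05 test is that of the primary outcome in the ITT set, with per protocol as a sensitivity analysis.
2. Complete ablation is the single key secondary outcome. It is judged by whether the confidence limit for the between-arm difference excludes a 15-point deficit, and is reported in both the ITT and per-protocol sets. The level should be the one-sided 5% that reproduces the 54 patients (lower limit of a two-sided 90% interval). If one-sided 2.5% is preferred, restate the Sample size section as about 34 per arm; the resulting 68 still fits within 80, leaving 12 spare.
3. All other secondary outcomes, including the stated aims of stay, mortality and quality of life, remain secondary. They are reported as between-arm estimates with 95% confidence intervals, stated to be unadjusted for multiplicity, and are not used for confirmatory claims. Relabelling the stated aims as exploratory is not needed.

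The cost is a few sentences, with no added patients, visits or data. The downside is that the sponsor gives up calling single secondary outcomes significant.

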##### Sample size

Based on a previous study from our center, the primary outcome (any complication Grade 2 or above, Clavien-Dindo Classification) occurred in 45% of patients undergoing open ablation. The similar complication rate from another external study was 39.5%. The hypothesis is that with a laparoscopic approach, the complication rate can be reduced to 10%. With an alpha of 5% and power of 80%, we will need 60 patients (30 in each arm).

The rate of complete ablation in one month is approximately 95% for open ablations. Using a non-inferior approach and assuming a similar rate of complete ablation in the laparoscopic group, we will need 54 patients (non-inferiority limit 15%, alpha 5% and power 80%).

By including 80 patients, both above sample-size calculations will be covered, and we will have sufficient material compensate for possible excluded patients. Before randomization, we will perform training of laparoscopic ablation using a training fantom developed for the purpose. Accuracy of laparoscopic needle placement with ultrasonography will be assessed using a gel with artificial tumors and an artificial abdominal wall. In addition, we will perform 20 cases with laparoscopic ablation to ensure that technique and learning curve is sufficient compared with our standard of care (open ablation). At this point, sufficient safety and efficacy (comparable to the literature) will be

ensured prior to randomization and additional cases and additional training may be performed is necessary.

After randomization of the first 15 laparoscopic cases, we will perform an interim analysis looking only at conversion rates in the laparoscopic group due to lack of feasibility. In case of a conversion rate above 20%, sample size will be increased according to the conversion rate, e.g. 20% more patients in each group with a conversion rate of 20%. This is done to ensure sufficient power in our comparison between the open and laparoscopic technique.

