## 3. Method

The study is a randomized, controlled, multicenter study in patients with liver malignancies treated at the four Danish liver surgery centers (Rigshospitalet, Odense, Århus and Aalborg). Patients with one or more liver tumor suitable for ablation as primary treatment, but not amenable for percutaneous ablation will be randomized between laparoscopic and open ablation. Opaque envelopes with patient numbers containing the randomization sequence will be opened after informed consent has been obtained. We plan to include 80 patients with 40 patients per arm. Patients will be randomized 1:1 (see below). Randomization will be stratified on center level to ensure comparable populations between the groups within each center.

Due to perioperative findings, the treatment to which the patient is randomized to may be considered not feasible or inappropriate, e.g. due to insufficient visualisation of tumor or findings that warrant a different treatment strategy. In these cases, the treatment strategy is based on the surgeons preferences. In laparoscopic cases, a minimally invasive approach should be maintained if possible, e.g. by combining laparoscopy with percutaneous ablation needle placement.

Ninety days after the procedure, the patient chart will be evaluated to register patient characteristics and outcomes. Moreover, at one month all patients will receive a CT-scan to evaluate success rate (complete ablation response). The CT-scan is part of standard of care, it is assessed by an experienced radiologist, and it is not part of this study. Before surgery and one month after, health related quality of life (HRQoL), the psychological burden and level of recovery will be assessed. Open ablation is standard of care. Thus, the intervention group will receive a treatment with assumed fewer complications and similar success rate.

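### The 54 patients stated for non-inferiority of complete ablation do not give 5% alpha and 80% power together; the planned 80 just suffice, with essentially none spare for exclusions

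*Combined protocol and SAP*

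**What the plan says.** The Sample size section takes an open success rate from the literature ("The rate of complete ablation in one month is approximately 95% for open ablations") and sets the laparoscopic rate equal to it ("assuming a similar rate of complete ablation in the laparoscopic group"). With "non-inferiority limit 15%, alpha 5% and power 80" per cent, it concludes that "we will need 54 patients".

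The same section then states: "By including 80 patients, both above sample-size calculations will be covered". It adds that the total also compensates for patients who may be excluded. No exclusion rate is given. Section 3 (Method) fixes the total: "We plan to include 80 patients with 40 patients per arm".

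Section 4 (Statistical considerations) names no non-inferiority test and no confidence interval. Complete ablation is a dichotomous secondary outcome, and for those "rates of secondary dichotomous outcomes will be compared between the groups using Fischer's exact test". A general p < 0.05 rule applies, with no statement on sidedness. Analyses are planned on both the intention-to-treat and the per-protocol level.

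**The concern.** Success of 95% lies close to the upper limit of 100%. With 27 patients per arm the expected number of failures is 27 × 0.05 = 1.35 per arm, too few for a normal approximation with unpooled variance. A sample size from that approximation may carry a real error rate and power different from those stated.

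Two things follow. First, the step from 54 to 80 reads as a reserve of 80 − 54 = 26 patients for this outcome. If the true requirement is nearer 80, the reserve does not exist, and losses in the per-protocol set reduce power below target. Second, the analysis section provides no way to reach a non-inferiority conclusion. Fisher's test asks whether the rates are equal, and a non-significant result would not show that laparoscopy is within 15 points of open ablation. Sections 6 and 14 name a lower success rate as the main possible disadvantage to patients, so what may be concluded on this outcome matters, although it is secondary.

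**Working it through.** **Inputs.** From the Sample size section: success 95% in both arms, margin 15 points (read as absolute), alpha 5%, power 80%. From section 3: 1:1 allocation, 40 per arm. Sidedness is not stated; one-sided 5% is inferred in step 1.

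**Step 1: reproduce the plan's figure.** Unpooled Wald formula, one-sided 5%:

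n per arm = (1.645 + 0.842)² × 2 × 0.95 × 0.05 / 0.15² = 6.185 × 0.095 / 0.0225 = 26.1, so 27 per arm and **54 in total**, as stated.

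At one-sided 2.5% the formula gives 33.1, so 34 per arm and 68 in total, which does not match. The plan's alpha is therefore one-sided 5%.

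**Step 2: exact behaviour at 27 per arm.** Every pair of binomial outcomes was enumerated. Power is at 95% v 95%; type I error is at the margin, 80% laparoscopic v 95% open.

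| Test, one-sided 5%, 27 per arm | Power | Type I error at 80% v 95% |
|---|---|---|
| Wald | 80.5% | 7.7% (maximum over the null 8.6%) |
| Farrington-Manning score | 61.8% | 4.2% (maximum over the null 6.4%) |

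An exact unconditional version of the score test also has 61.8% power. The Neyman-Pearson upper bound for any test that holds 5% is 69.7%. So no choice of valid test gives both 5% and 80% with 54 patients.

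**Step 3: the size that a score test needs.** The Farrington-Manning formula uses the null variance at the restricted estimates, here 82.3% and 97.3%:

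- null SD = √(0.823 × 0.177 + 0.973 × 0.027) = 0.415
- alternative SD = √(2 × 0.95 × 0.05) = 0.308
- n per arm = [(1.645 × 0.415 + 0.842 × 0.308) / 0.15]² ≈ 39.4, so 40 per arm and **80 in total**.

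Enumeration at 40 per arm gives 81.9% power for both the score test and its exact version. The score test's type I error there is 4.2% at 80% v 95% (maximum 5.3%).

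**Step 4: power when patients are lost.** The documents give no exclusion rate, so these losses are assumptions. Score test, one-sided 5%:

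| Evaluable, laparoscopic v open | Assumed loss | Power |
|---|---|---|
| 40 v 40 | none | 81.9% |
| 36 v 36 | 10% | 78.6% |
| 34 v 34 | 15% | 75.5% |
| 32 v 32 | 20% | 76.9% |
| 32 v 40 | 20% of the laparoscopic arm, e.g. outside the per-protocol set | 72.8% |

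Power does not fall smoothly with n because the outcome is discrete.

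**Step 5: if a two-sided 95% interval is meant.** At one-sided 2.5%, 40 per arm gives 71.4%.

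**The case against.** The strongest reply is that 54 contains no arithmetic slip. It follows exactly from a standard formula, the plan recruits 80 rather than 54, and 80 reaches the stated target with a sound test. All of that stands. A reader might infer that 80 patients do not cover the non-inferiority calculation. At the plan's own alpha the documents do not support that: 81.9% power with complete data meets the 80% target. Only the spare room fails.

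A reader might also take 76 (38 per arm) as the true requirement, leaving four spare patients, because score-test power there is 83.0%. That is a favourable point on a saw-toothed curve: 36 and 37 per arm give 78.6% and 78.1%. At 38 per arm the type I error is 5.07% at 80% v 95% (maximum 6.15%), and the exact test has 77.6% power. About 80 is the defensible figure.

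Nor do the documents support calling the trial underpowered on the strength of the 71%. That figure assumes one-sided 2.5%, whereas the plan states 5% and 54 reproduces only at one-sided 5%.

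The score test itself slightly exceeds 5% at some null rates, so its advantage over Wald is one of degree. The difference is still material: at 40 per arm the Wald test has 7.1% type I error at 80% v 95%, against 4.2% for the score test.

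Finally, losses may be small. The one-month CT is standard of care for all patients, and the sample size is to be increased if conversion exceeds 20%. That limits the practical shortfall. It does not supply the stated reserve, since conversion at or below 20% triggers no increase and can still reduce the per-protocol set.

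**Conclusion.** The point holds in a limited form. The stated 54 does not deliver 5% alpha and 80% power together: at that size one has either 80.5% power with 7.7% type I error (Wald) or 61.8% power (score test). About 80 evaluable patients are needed at one-sided 5%, so the planned total just covers this secondary outcome and the implied reserve of 26 is essentially zero. On assumed losses of 10 to 20%, power is about 73 to 79%, a modest shortfall. Separately, the analysis section names no method that tests the 15-point margin.

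This rests on an absolute margin, 95% success in both arms and one-sided 5%. That the plan used the Wald formula is inferred from the exact match, because no method is named. The primary-outcome calculation is not affected.

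**What to change.** Keep 80 patients and change the wording in two places.

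- **Section 4, Statistical considerations:** take complete ablation out of the outcomes compared by Fisher's test. Analyse it with a Farrington-Manning or Miettinen-Nurminen interval for laparoscopic minus open success, and conclude non-inferiority if the lower limit lies above -15 percentage points. State the level: one-sided 5%, that is, a two-sided 90% interval.
- **Sample size:** replace 54 with about 80 evaluable patients (40 per arm, power about 82% with the score test). Keep the statement that 80 covers this calculation, and remove the claim of an allowance for exclusions as far as this outcome is concerned. If a two-sided 95% interval is intended instead, say so and report power of about 71% at 40 per arm.

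The cost is wording only, with no extra patients. The drawback is that the stated figure becomes less favourable: the plan would show this outcome meeting its target only with nearly complete data.

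### The conversion check is a single look at 15 laparoscopic patients and appears to count only conversions for lack of feasibility, so it can miss dilution that it is meant to correct

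*Combined protocol and SAP*

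**What the plan says.** The Sample size section sets 30 patients per arm for the primary outcome ("With an alpha of 5% and power of 80%, we will need 60 patients (30 in each arm") and recruits 40 per arm, so that both calculations are covered and exclusions can be absorbed. Once 15 patients have been allocated to laparoscopy, a check follows, described thus: "we will perform an interim analysis looking only at conversion rates in the laparoscopic group due to lack of feasibility". If the rate is above 20%, both groups are enlarged by the conversion rate; the worked example adds 20% at a rate of 20%. The purpose is given as "This is done to ensure sufficient power in our comparison between the open and laparoscopic technique". No later look is described, although about 25 further laparoscopic patients follow.

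Section 3 (Method) gives wider grounds for leaving the allocated treatment, which "may be considered not feasible or inappropriate, e.g. due to insufficient visualisation of tumor or findings that warrant a different treatment strategy". The Secondary outcomes list "Conversion rate in the laparoscopic group" with no restriction on reason. Section 4 names Fisher's exact test for the primary outcome and analyses both by intention to treat and per protocol.

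**The concern.** The check exists to protect power, and two features limit its ability to do so.

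- **One small sample.** Fifteen patients give a very imprecise rate, and the question is not asked again.
- **A narrower count than the problem.** Under intention to treat, a laparoscopic-allocated patient who ends with open surgery can carry open-surgery risk, whether the surgeon converted because the tumour could not be seen or because of another finding. Taken as a filter, the words on lack of feasibility leave the second kind out.

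If conversion is high and the check stays silent, the trial finishes at 40 per arm with a diluted difference.

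**Working it through.** **Inputs from the documents.** Complications "occurred in 45% of patients undergoing open ablation"; the hypothesis is that with laparoscopy "the complication rate can be reduced to 10" percent. Planned size is 40 per arm, one look at 15, and an increase to N × (1 + observed rate). Sidedness is not stated; two-sided 5% is used because it reproduces the plan's figure.

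**Assumptions, because the documents give no figure.** True conversion rate c; share f of conversions that count as lack of feasibility; complication risk r in converted patients.

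**Step 1. The plan's own figures.** Mean proportion 0.275, difference 0.35:

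n₀ = [1.96√(2 × 0.275 × 0.725) + 0.842√(0.45 × 0.55 + 0.10 × 0.90)]² / 0.35² = 24.3

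With continuity correction: n = (n₀/4)[1 + √(1 + 4/(0.35 n₀))]² = 29.8, so 30 per arm. This reproduces the plan.

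Non-inferiority ("we will need 54 patients (non-inferiority limit 15%, alpha 5% and power 80" percent): (1.645 + 0.842)² × 2 × 0.95 × 0.05 / 0.15² = 26.1, so 27 per arm, or 54. This also reproduces.

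**Step 2. How often the check stays silent.** The count is binomial with n = 15 and probability f × c. Three of 15 is exactly 20%: above 20% excludes it, while the worked example includes it. Both readings are shown, each at c = 25% / c = 30%.

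| Share counted, f | Silent at 3 or fewer | Silent at 2 or fewer |
|---|---|---|
| All | 46% / 30% | 24% / 13% |
| Three quarters | 69% / 55% | 45% / 31% |
| Two thirds | 77% / 65% | 53% / 40% |
| Half | 89% / 82% | 71% / 60% |

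The exact 95% interval for 3 of 15 is 4% to 48%. At c = 40% with all conversions counted, the check is silent only 9% of the time (3 or fewer).

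**Step 3. Power at 40 per arm if there is no increase.** The laparoscopic rate becomes 0.10(1 − c) + r c. For example, at c = 0.30 and r = 0.45 it is 0.07 + 0.135 = 20.5%. Power is by exact enumeration of the two-sided Fisher test against 45%.

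| c | r = 45% | r = 31% | r = 27.5% |
|---|---|---|---|
| 0 | 93.5% | 93.5% | 93.5% |
| 10% | 84% | | |
| 25% | 64% | 78% | 81.5% |
| 30% | 56.5% | 74% | 78.3% |

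**Step 4. What the fix gains.** Average power is the sum, over possible counts, of the probability of the count times the Fisher power at the resulting N, with r = 45%. The second look uses the first 30 laparoscopic patients cumulatively (more than 6 of 30). An increase already triggered at 15 stands.

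| Rule (3 of 15 not a trigger) | c = 25% | c = 30% |
|---|---|---|
| One look, two thirds counted | 67.4% | 61.8% |
| One look, all counted | 72.3% | 68.2% |
| Looks at 15 and 30, all counted | 74.6% | 70.5% |

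- Both changes together: 74.6 − 67.4 = 7.2 points, and 70.5 − 61.8 = 8.7 points.
- Second look alone: 74.6 − 72.3 = 2.3 points, and 70.5 − 68.2 = 2.3 points.
- With all conversions counted, the second look cuts silence from 46% to 28% at c = 25%, and from 30% to 12% at c = 30%.
- At c = 10%, the chance of an unneeded increase rises from 5.6% to 6.7%.

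**Step 5. The ceiling.** At c = 30%, even a certain trigger at the true rate gives 40 × 1.30 = 52 per arm and 70% power. At c = 25% it gives 50 per arm and 76%.

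**The case against.** A reader might infer that the trial is heading for 57% power, or that a second look would restore 80%. The documents support neither.

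- **No expected conversion rate is given.** The 25% and 30% are assumptions. The plan includes phantom training, 20 laparoscopic cases before randomization with more if needed, and 10 patients per arm above the calculated 30. At 10% conversion, power is still 84%. This stands, with the limit that those 10 are also meant to cover exclusions.
- **The 45% risk in converted patients is a worst case.** At 27.5%, power without an increase is 81.5% at 25% conversion. This stands, and it is why a range is shown.
- **Reading 3 of 15 as a trigger gives the single look about the protection that a second look would add** (24% and 13%, against 28% and 12% for two looks under the stricter reading). This stands for sampling error, but it does not cure a narrow count: the misses are then still 53% and 40% at a two-thirds share.
- **The feasibility words may explain why the check is made, without filtering what is counted.** This is possible. A finding that changes strategy also need not end in open surgery, since Section 3 asks for a minimally invasive approach to be kept where possible. If so, deleting the words loses nothing, and the single-look weakness remains.
- **One early check is a reasonable choice in an investigator-initiated trial of 80 patients.** This is fair, but the extra count uses data that are already recorded.

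**Conclusion.** The point holds as a limited weakness in a safeguard. It is not evidence that the trial is underpowered. At assumed true conversion of 25% to 30%, the single look is silent 30% to 46% of the time if 3 of 15 does not trigger, and 13% to 24% if it does. It is silent more often if some conversions are left out of the count. The cost in power depends on the assumed risk in converted patients: at 40 per arm, roughly 57% to 64% at a 45% risk and 74% to 78% at 31%. At conversion near 10% the planned size copes, and near 40% the check usually triggers if every conversion is counted.

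Most of the gain comes from counting every conversion to open surgery; the second look adds about 2 points. Under the 45% assumption, average power stays below 80% even with both changes, because the size of the increase is a separate limit.

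**What to change.** Make two changes in the Sample size section.

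1. Remove the restriction to lack of feasibility. Count every laparoscopic-allocated patient whose operation ends as an open procedure, for any reason. Operations kept minimally invasive, such as laparoscopy combined with percutaneous needle placement, are not counted.
2. Keep the look at 15 and apply the same rule once more, cumulatively, when the first 30 laparoscopic-allocated patients have been operated on. Recruitment continues meanwhile.

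In the same edit, state whether exactly 20% triggers the increase, since the rule and its example differ.

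Only conversion is inspected and no outcomes are compared between arms, so there is no alpha cost. The surgeon's decision to convert is untouched. The cost is a short protocol edit and one extra count. The drawbacks are that the final size may be settled only at about 60 of 80 patients, and that the existing increase is triggered slightly more often (5.6% to 6.7% at 10% conversion).
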